9.8.4 Vital Signs

Observed values, baseline and changes from baseline will be summarized by visit for each vital sign parameter.

The number (%) of subjects meeting the following criteria at any time after the start of dosing will also be tabulated for systolic BP, diastolic BP and pulse:

- All values within 20% of change from baseline
- At least one value $\geq 20\%$ reduction from baseline, but no increases $\geq 20\%$ from baseline
- At least one value $\geq 20\%$ increase from baseline, but no reductions $\geq 20\%$ from baseline
- At least one value $\geq 20\%$ reduction from baseline and at least one value $\geq 20\%$ increase from baseline

This summary will present data for the first 24 weeks, first 48 weeks and the whole study.

Values displaying a $\geq 20\%$ change from baseline will be flagged in the listings, with the flag identifying if it is a reduction or increase from baseline.

9.8.5 Twelve-Lead Electrocardiogram

Observed values, baseline and changes from baseline will be summarized by visit for each ECG parameter.

The number (%) of subjects meeting the following criteria at any time after the start of dosing will also be tabulated:

Maximum PR interval

- < 170ms
- \geq 170ms

Also

- All values within 20% of change from baseline
- At least one value \geq 20% reduction from baseline, but no increases \geq 20% from baseline
- At least one value \geq 20% increase from baseline, but no reductions \geq 20% from baseline
- At least one value \geq 20% reduction from baseline and at least one value \geq 20% increase from baseline

Heart Rate

- All values within 20% of change from baseline
- At least one value \geq 20% reduction from baseline, but no increases \geq 20% from baseline
- At least one value \geq 20% increase from baseline, but no reductions \geq 20% from baseline
- At least one value \geq 20% reduction from baseline and at least one value \geq 20% increase from baseline

Maximum QTcF

- < 450ms
- \geq 450ms

Maximum increase from baseline in QTcF

- < 30ms
- 30ms - < 60ms
- \geq 60ms

This summary will present data for the first 24 weeks, first 48 weeks and the whole study.

The number (%) of subjects with ECG results in the following categories (per the investigator's interpretation) will be presented by visit/time point:

- normal
- abnormal - not clinically significant
- abnormal - clinically significant

The listing of ECG data will present the replicate data separately from the 'mean of replicate' data.

Values meeting the criteria of potential concern above will be flagged in listings.

Further analyses of QT, QTcF and Heart Rate, and PK:PD modelling investigating any relationship with exposure will be detailed in a separate QT analysis plan for the project and reported in a separate ECG report.

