1.3.3. Duchenne Muscular Dystrophy Patients Safety Summary

Thirty-two boys with DMD have taken part in three studies with SMT C1100. However as several of the boys have taken part in more than one study, 22 individual boys with DMD have been exposed to SMT C1100 in total.

In Study SMT C11002 (F2) involving 12 paediatric patients with DMD, SMT C1100 was well tolerated, with the majority of reported AEs being mild in severity. No severe AEs or SAEs were reported. The most frequently related drug-related AEs were pale stools, which were predominantly reported at the higher dose intervals of 0.1 g/kg *bid* and 0.1 g/kg *tid*. In study SMT C11002 at doses of up to 0.1 g/kg *bid* there were no significant QTc changes in ECGs. Only one patient had an increase from baseline ≥ 30 ms in the QTcF although all his QTcF values were <400 ms.

In Study SMT C11003 (F3) all 12 patients experienced at least one TEAE while receiving each of the three treatments, including placebo. It is important to note that placebo included excipients to mimic pale stool colour in order to maintain the blind. There were no severe or serious AEs, and no patient discontinued due to an AE. All AEs were considered mild or moderate by the investigator. The most common TEAE in the study, was pale stools, reported by all twelve patients (100%) receiving SMT C1100 and 9 patients (75%) receiving placebo.

ECG data for study SMT C11003 showed that in neither the placebo nor active groups did any patient display a maximum increase in QTcF of ≥ 60 ms. Nine (75%) patients in the placebo group had a maximum increase in QTcF of between 30–59 ms, compared to four (33%) patients in the 1.25 g *bid* group and three (25%) patients in the 2.5 g *bid* group. The maximum QTcF (average of replicates) recorded was 453 ms seen at the 2.5 g *bid* level. Mean increases from baseline were less than 10 ms for all groups, except the placebo group, across all time points. No significant difference was seen between the active and placebo groups for median changes in heart rate.

Overall, SMT C1100 was considered safe and well tolerated in study SMT C11003 in paediatric patients with DMD.

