5.2.1.2. Exclusion Criteria

To be enrolled patients must not meet any of the selected criteria for their cohort:

Criterion Number	Criterion	Cohort 1	Cohort 2	Cohort 3
1	Have physical exam findings that in the investigator's opinion should be exclusionary e.g., lower limb injury that may affect 6MWD performance	✓	✓	✓
2	Have any change (initiation, change in type of drug, dose modification, schedule modification, interruption, discontinuation or reinitiation) in prophylaxis/treatment for congestive heart failure (CHF) within 3 months prior to the start of study treatment	✓	✓	✓
3	Have uncontrolled clinical symptoms and signs of CHF (American College of Cardiology/American Heart Association Stage C or Stage D)	✓	✓	✓
4	Have abnormal GLDH at baseline (>1.5 x ULN)	✓	✓	✓
5	Have abnormal coagulation times at baseline (>1.5 x ULN)		✓	✓
6	Have an abnormal ECG e.g., a QTcF >500 ms, left bundle-branch block or any other major conduction defect	✓	✓	✓
7	Use beta blockers (however, if during the course of the study they are clinically indicated they can be initiated)	✓	✓	NA
8	Use herbal supplements and be unwilling to stop these for the duration of the study	✓	✓	✓
8	Have a known hypersensitivity to any of the ingredients or excipients of the IMP. microfluidised oral suspension (F3): Poloxamer 188, Methylparaben, Propylparaben, Hydroxypropylmethyl cellulose, Glycerol, Non crystallising sorbitol [70%], Xanthan gum, Strawberry cream flavour [PHS-132963]	✓	NA	✓
10	Have a known hypersensitivity to any of the ingredients or excipients of the IMP. Powder for oral suspension (F6): hypromellose acetate succinate	NA	✓	NA
11	Have been exposed to another investigational drug or DMD interventional agent within 3 months prior to start of the Treatment Phase. Prior exposure to SMT C1100 or participation in an approved deflazacort access program (e.g., FOR-DMD or ACCESS DMD clinical trials) within this period would not exclude the patient (provided they have been on stable treatment for 6 months)	✓	✓	✓

Study Number: SMT C11005	Compound No.: SMT C1100
Protocol	Version: 5.0 24Feb2017

Criterion Number	Criterion	Cohort 1	Cohort 2	Cohort 3
12	Have a history of major surgical procedure within 12 weeks prior to the start of the Treatment Phase (Week 1)	✓	✓	✓
13	Be undertaking ongoing immunosuppressive therapy (other than corticosteroids)	✓	✓	✓
14	Have an expectation of a major surgical procedure (e.g., scoliosis surgery) during the 12-month Treatment Phase of the study	✓	✓	✓

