6.4. Safety Procedures

6.4.1. Twelve-Lead Electrocardiogram

Twelve-lead ECGs will be performed at the times outlined in the Time and Events Table. A single ECG (in triplicate) will be performed at Screening, Baseline, Weeks 12 and 36. At Weeks 1, 24 and 48 ECGs will be performed pre-AM dose and 0.5, 2, 4 and 6 h post-AM dose or pre-PM dose and 0.5, 2 and 4 h post-PM dose.

TriPLICATE ECGs separated by approximately 2 to 5 minutes should be collected at each time point. The ECGs will be transmitted on an ongoing basis to a centrally based cardiologist who will independently examine the ECGs. Further details on performing and transmitting ECGs can be found in the Study Reference Manual.

Measurements will be made using an ECG machine that automatically calculates the heart rate and measures PR, RR, QRS, and QT.

All ECG traces will be reviewed and signed by the PI or a Study Physician and any abnormalities will be marked as clinically significant or not clinically significant. If the average QTc(F) is \geq 500 ms then an additional ECG should be repeated after at least a 5-minute interval.

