5.4.4 Twelve-Lead Electrocardiogram (ECG)

Triplicate ECG measurements will be taken at screening, baseline, end of study, Day 1 and Weeks 12, 24, 36 and 48 during the first 48 weeks and then 6 monthly during the extension phase. If a subject withdraws from the study prematurely they will also be assessed at the termination visit.

Cohorts 1 and 2

On Day 1 and at Weeks 24 and 48 the measurements will be taken at either pre-AM dose and 0.5, 2, 4 and 6h post-AM dose OR pre-PM dose and 0.5, 2 and 4h post-PM dose. At Weeks 12 and 36 the measurements will be taken at 4h post-AM dose.

Cohort 3

At Weeks 12, 24, 36 and 48 the measurements will be taken at pre-AM dose and 0.5, 2, 4 and 6h post-AM dose.

Extension Phase

At Week 48 (start of extension phase) the measurements will be taken at 0.5, 2, 4 and 6h post-AM dose. Then measurements will be taken at 4h after dosing at each 6 monthly visit.

Heart rate, PR interval, RR interval, QRS complex and QT interval will be recorded. Heart rate corrected QTc will be determined using Fridericia (QTcF) and Bazett (QTcB) formulae.

The average of the triplicate measurements will be used in the summaries of data by visit, however individual replicates and unscheduled data will be used in categorical analyses (e.g. determining number

of subjects with a QTcF \geq 60ms). A categorical analysis will also be conducted based on the averages of the triplicate measurements.

Changes from baseline will be calculated for averaged triplicate data and for individual replicate data.

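### The absolute QTcF table in SAP 9.8.5 has one cut at 450 ms and no baseline shift, so it cannot separate new crossings from pre-existing values or show who reached 500 ms

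*SAP*

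**What the plan says.** SAP 9.8.5 introduces its categorical ECG table with "The number (%) of subjects meeting the following criteria at any time after the start of dosing will also be tabulated". Absolute maximum QTcF is split once, at 450 ms. Directly below, under "Maximum increase from baseline in QTcF", come three rows: <30, 30 to <60 and ≥60 ms. Values meeting the criteria are flagged in listings, replicates and means are listed separately, and further QT work is left to a separate QT analysis plan that is not among the documents.

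SAP 5.4.4 sets the data that feed the table: "individual replicates and unscheduled data will be used in categorical analyses". It continues: "A categorical analysis will also be conducted based on the averages of the triplicate measurements". On changes it says: "Changes from baseline will be calculated for averaged triplicate data and for individual replicate data".

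The protocol works at a different level. Exclusion criterion 6 (section 5.2.1.2) reads: "Have an abnormal ECG e.g., a QTcF >500 ms, left bundle-branch block or any other major conduction defect". Section 6.4.1 deals with an average QTcF of 500 ms or more: "then an additional ECG should be repeated after at least a 5-minute interval".

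**The concern.** The single cut lies 50 ms below the entry limit (500 − 450 = 50). Any boy enrolled at 450 to 500 ms meets the criterion from his first ECG on drug unless his value drops, so the row mixes what he brought with him and what happened on treatment. At the other end, the row cannot show whether anyone newly reached 480 or 500 ms.

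A second issue is the unit of counting. In the replicate version, one reading among dozens is enough to make a boy a case.

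The stakes are moderate. Protocol 1.3.4 names hERG inhibition by the metabolites as one of three potential drug-related risks, describes the population as prone to ECG abnormalities, and gives frequent ECGs as the precaution. There is no control arm against which to read a raw count.

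**Working it through.** The documents state no error rate or precision for this table, so there is no figure of theirs to reproduce.

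**1. Thresholds side by side**

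| Place | QTcF level |
|---|---|
| Exclusion criterion 6 | >500 ms |
| Repeat ECG, Protocol 6.4.1 | average ≥500 ms |
| Healthy-volunteer summary, Protocol 1.3.2 | >480 ms |
| Earlier study in boys (SMT C11004), Protocol 1.3.3 | >450 ms |
| SAP 9.8.5, absolute row | 450 ms only |

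**2. Scheduled on-drug readings per boy to Week 48** (SAP 5.4.4; Day 1 pre-dose excluded; three replicates each)

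- Cohorts 1 and 2, AM series (Day 1, Weeks 12, 24, 36, 48): 4 + 1 + 5 + 1 + 5 = 16 time points, 16 × 3 = 48 replicates.
- Cohorts 1 and 2, PM series: 3 + 1 + 4 + 1 + 4 = 13 time points, 13 × 3 = 39.
- Cohort 3 (Weeks 12, 24, 36, 48): 5 × 4 = 20 time points, 20 × 3 = 60.

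Unscheduled ECGs and the end-of-study ECG would add to these.

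**3. Chance of being counted with no drug effect**

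The documents give no QTcF SDs, so these are assumptions. Model: reading = constant true QTcF μ + time-point error (SD s_t) + replicate error (SD s_r). The pairs (s_t, s_r) are 5/5, 8/6 and 10/8 ms. T is the number of time points, Φ and φ the standard normal distribution function and density.

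- Triplicate mean: 1 − Φ((450 − μ)/√(s_t² + s_r²/3))^T.
- Single replicate: 1 − [∫ Φ((450 − μ − s_t·u)/s_r)³ φ(u) du]^T.

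Example on means, μ = 430, SDs 8/6, T = 16: √(64 + 36/3) = 8.72; 20/8.72 = 2.29; tail probability 0.011; 1 − 0.989^16 ≈ 0.16.

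Simulation with 50,000 boys per setting gives the following for T = 16. Direct evaluation of the two formulas agrees to within 0.3 percentage points.

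| True QTcF | Single replicate ≥450 ms, % (5/5, 8/6, 10/8) | Triplicate mean ≥450 ms, % |
|---|---|---|
| 410 ms | 0.0 / 0.2 / 3.8 | 0.0 / 0.0 / 0.2 |
| 420 ms | 0.1 / 5.7 / 32.2 | 0.0 / 0.5 / 5.1 |
| 430 ms | 9.8 / 58.0 / 88.9 | 0.4 / 16.1 / 43.4 |
| 440 ms | 95.7 / 99.6 / 100 | 49.4 / 88.4 / 96.0 |
| 450 ms | 100 / 100 / 100 | 100 / 100 / 100 |

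At 430 ms with SDs 8/6, the schedule moves the single-replicate rate from 50.2% (T = 13) to 58.0% (16) and 66.1% (20). On means it moves from 13.2% to 16.1% and 19.8%. At 410 ms the single-replicate rate never exceeds 4.8% in any setting tried.

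Two things follow. Noise matters mainly from about 420 ms upward. Averaging does not help a boy whose true value is already 450 ms; only a baseline shift does.

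**4. The increase rows**

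With T = 16 and a triplicate-mean baseline, an increase of ≥30 ms arises with no effect in 1.7 / 19.6 / 41.9% of boys by single replicate and in 0.2 / 7.1 / 20.0% by mean. SAP 5.4.4 does not say which baseline applies to a replicate-level change; SAP 5.1 gives only the last non-missing assessment before first dose.

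Protocol 1.3.3 shows that counts based on a maximum can be high without drug: "Nine (75%) patients in the placebo group had a maximum increase in QTcF of between" 30 and 59 ms, that is 9/12 = 75%, against 4/12 = 33% and 3/12 = 25% on the two active doses.

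**The case against.** A reader might infer that the ECG table ignores baseline altogether, rests only on single replicates and would hide an extreme value. The documents do not support that.

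- The increase rows in the same table carry baseline information. A boy who enters and stays at 460 ms shows as ≥450 ms but <30 ms increase.
- The triplicate-mean categorical analysis is already planned.
- SAP 9.1 requires the minimum and maximum for continuous variables, and by-visit ECG summaries use triplicate averages. An average of 520 ms at a summarised visit would print as that visit's maximum, and it would also be flagged in the listing.
- Protocol 6.4.1 provides triplicates, independent review by a central cardiologist, investigator grading and a repeat at an average of 500 ms or more.

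It is also fair to say that entrants at 450 to 500 ms are hypothetical. No baseline QTcF distribution is given, no boy in SMT C11004 exceeded 450 ms, and the highest replicate average in SMT C11003 was 453 ms. Exclusion criterion 16 also lets the investigator exclude on ECG findings. The placebo figure is weak evidence for replicate noise in particular: the same summary reports mean increases below 10 ms in all groups except placebo, which may point to a systematic shift, and does not say whether single replicates were used. The separate QT plan may contain more.

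These points narrow the issue but do not remove it. By-visit maxima and listings are not counts of boys. The increase rows do not show who crossed a level. The mean-based version has no other cut specified. The QT plan, whatever it holds, does not change the table specified here.

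**Conclusion.** The point holds in a limited form. The absolute QTcF row has one cut, below the level the protocol itself uses, with no shift from baseline and no ≥480 or ≥500 ms row. It counts a pre-existing value as an on-drug case, and no planned table in the SAP counts boys newly crossing a level. Sections 5.4.4 and 9.8.5 also leave open whether the replicate or the mean version is the main one.

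The rows and levels can be checked in the text and need no assumption. The size of the noise component rests entirely on assumed SDs, and the number of boys affected cannot be computed without a baseline distribution. This is a minor safety-reporting point in an unpowered, open-label exploratory study.

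**What to change.** In SAP 9.8.5, replace the single absolute split with a table of baseline category by worst post-dose category for QTcF: <450, 450 to <480, 480 to <500 and ≥500 ms. All three cut-offs already appear in the documents. New crossings then stand apart from pre-existing values.

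Name the planned triplicate-mean version as the main table, and state that the mean pre-dose triplicate is the baseline for changes. Keep the single-replicate and unscheduled version as supportive. While editing 5.4.4, reword its example, which gives ≥60 ms as a QTcF value where an increase is evidently meant.

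The cost is a table-shell change and a few lines of programming on data already collected. The downside is a few more rows and fewer boys flagged in the main table; single-replicate cases remain in the supportive table and the listings.

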9.8.6 Echocardiogram (Cohorts 1 and 2)

The observed values and changes from baseline will be summarized for each parameter (LVEF and SF) by visit.

The number (%) of subjects with normal and abnormal assessments will be tabulated by visit.

9.8.7 Physical Examination

Weight and BMI values and changes from baseline in weight and BMI will be summarized by visit.

The number (%) of subjects with physical examination results in the following categories will be presented by body system and visit:

- normal
- abnormal - not clinically significant
- abnormal - clinically significant

9.8.8 Pulmonary Assessment

The predicted spirometry assessments will be adjusted for age and sex by the site. Assessments will be adjusted for race as shown in the [Table 1](#) of Section 6.4.5 in the protocol. The observed values and changes from baseline will be summarized for each parameter by visit.

Individuals data will be plotted over time for each parameter and box and whisker plots will be presented for the changes from baseline against visit.

9.9 Pharmacokinetic Analyses

Plasma concentrations of SMT C1100, DHDI and DHDIII will be summarized (n, median, minimum and maximum) by cohort, visit and time-point. The summaries will also present the median and the number of subjects who have plasma concentrations below the lower limit of quantification (LLOQ). The SMT C1100 summary will also include the number of subjects achieving SMT C1100 concentrations of ≥ 30 ng/mL and ≥ 70 ng/mL.

The concentration listings will present the data as <LLOQ with the actual limit of quantification value presented.

Individual concentration-time plots will be presented in trellis plots for SMT C1100 and metabolites separately. A log10 scale will be used for the concentration axis. The plots will identify the subject's cohort.

The metabolite ratios (DHDI/SMT C1100 and DHDIII/SMT C1100) will also be plotted over time and will be summarized by cohort, visit and time-point.

Pop-PK analyses are described in a separate Pop-PK analysis plan and may be reported separately.

Observed Week 12 C_{trough} and simulated C_{max} and C_{av} parameters will be summarized. The number of subjects achieving SMT C1100 levels ≥ 30 ng/mL, ≥ 70 ng/mL will also be reported for each parameter.

9.10 Relationship Analyses (Cohorts 1 and 2)

9.10.1 Relationship with SMT C1100 and Metabolite Exposures

The following Week 12, 24, 36 and 48 data will be plotted against SMT C1100 concentrations:

- MRI parameter changes from baseline (MRS fat fractions for the Vastus Lateralis and Soleus, and MRS T2 for Vastus Lateralis and Soleus)
- %MHCd change from baseline * (Weeks 24 and 48 only)

- Fibre diameter (mean) change from baseline * (Weeks 24 and 48 only)
- Utrophin intensity (mean) change from baseline * (Weeks 24 and 48 only)
- Utrophin heterogeneity score change from baseline * (Weeks 24 and 48 only)
- 6MWD change from baseline
- NSAA (total) change from baseline
- 10 metre walk/run duration change from baseline
- Time to stand change from baseline
- PUL total score change from baseline
- PODCI global function scale change from baseline

* based on average values across samples/sections ([Section 5.3.2](#)).

For a visit, the above response will be plotted separately with relevant observed Week 12 C_{trough} and the simulated parameters C_{max} and C_{av} .

The Pearson correlation coefficients (for each week) will also be presented in the footnote of the plots.

These plots will also be produced for the metabolites DHDI and DHDIII.

Any other exposure response modeling conducted will be reported separately.

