4.2.2. Individual Stopping Rules

The pharmacokinetics of SMT C1100 parent and metabolites, and their relationship with all safety parameters, will be reviewed on an ongoing basis by the Sponsor and the DMC. As this is an open-label study, the decision to stop individual patients may be made on a case-by-case basis. The DMC can also recommend, in individual patients, a lowering of the SMT C1100 dose.

If a patient's results meet either of the criteria below, dosing should be stopped and the tests should be repeated as soon as possible. If the repeated results still meet this criterion, the study drug will be permanently stopped and may not be restarted although the patient will continue to be followed for functional and MRI assessments for the duration of the study. If the patient is withdrawn from the study, a follow up visit should be arranged:

- GLDH \geq 3x ULN

Study Number: SMT C11005 Protocol	Compound No.: SMT C1100 Version: 5.0 24Feb2017
---	---

OR

- Bilirubin $\geq 2x$ ULN together with an INR $\geq 1.5x$ ULN (Cohort 2 and 3 only)

Any intolerable AE or SAE that is at least possibly related to study drug should lead to a temporary discontinuation of the patient's study treatment. After resolution of the intolerable AE or SAE, the Investigator, in discussion with the Sponsor, may decide to either permanently discontinue the patient's study treatment, or, if recommended by the DMC and Sponsor reinstate treatment but reduce their *bid* dose to 1.25 g for Cohort 1 and 3 or reduce the frequency to once-daily dosing (2.5 g or 1.25 g for Cohorts 1 and 3; 1 g for Cohort 2; see Section 8.1.1). If a lowered dose is tolerated for at least 2 weeks the Investigator can, based on the recommendation of the DMC and Sponsor escalate the dose up to the original strength. Once-daily dosing should occur in the morning.

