12.1.4.2. Pharmacokinetic Analyses

Plasma concentrations of SMT C1100 parent and metabolites will be summarised and plotted by time point. Using a model exposure parameters will be predicted for each subject at the relevant visits. These parameters will be used as the exposure parameters when investigating the relationships with other data.

Data will be summarised for each cohort separately, combining Cohorts 1 and 3 (F3 formulation), and over all patients.

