* Must be prior to dosing if time of assessment is recorded.

Windowing will not be used for the biopsy data as there is only one measurement post dose.

These visit windows will be reviewed and may be updated. Any assessments that fall outside of these windows will be reviewed on a case-by-case basis, and decisions on their handling will be fully documented prior to reporting.

Data will be included in analyses regardless of the duration of time since their last dose of study treatment and the assessment. However additional summaries may be generated excluding subjects if their assessment is performed several weeks after their last prior study dose. This will be reviewed on a case-by-case basis as the decision will be dependent on the assessment and the likely impact of the exclusion on the interpretation of the results.

Data collected outside these windows will only be listed.

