10.0 Changes from Planned Analyses

This analysis plan provides further information to that provided in the study protocol.

Changes from the planned analyses in the protocol include:

- [Protocol Section 12.1.3](#) states that, as the study is open-label, the data will be explored on a regular basis by the sponsor. A data access plan has been written that provides details concerning data accessibility to the study data by company individuals whilst the study is ongoing.
- [Protocol Section 12.1.4.2](#) mentions that PK parameters will be used as the exposure parameters when investigating the relationship with other data. Instead the maximum concentration recorded at the relevant visit will be used in these analyses.
- Cohort 3 efficacy data will not be combined with Cohort 1 and 2 data in any analyses.
- The SAP doesn't currently provide details concerning cardiac MRI parameters or the investigation of the relationship of exposure with changes in pulmonary function parameters and blood biomarkers. This detail will be added in a later version.

Important changes from [Version 1.0](#) of the SAP:

- Inclusion of Week 12 and Week 36 data in plots looking at the relationships between efficacy and pharmacodynamic endpoints and also their relationships with pharmacokinetic endpoints and demographics.
- Inclusion of all safety data for the first interim analysis.

- Exclusion of Dystrophin mutation type from the baseline disease characteristic summary.
- Inclusion of FOR-DMD subject's steroid data in steroid use summaries.
- Adjustment of windows to allow a wider window for Weeks 4 and 8, and to allow all available post baseline biopsy data to be included.
- Imputation method for missing activity scores from the NSAA which is only partially completed.

Important changes from [Version 2.0](#) of the SAP:

- Inclusion of fibre diameter and utrophin expression parameters.
- Functional endpoint data from Cohort 3 will not be combined with data from Cohorts 1 and 2.
- Clarification concerning the CSR when Cohorts 1 and 2 have completed their Week 48 visit.
- Inclusion of NSAA total score plots, sometimes replacing those for the NSAA linearized scores.
- Inclusion of waterfall plots, box and whisker plots and mean change from baseline plots for specified endpoints.
- Inclusion of PK parameters (observed [Week 12 C_{trough}] and simulated [C_{max} and C_{av}])
- Reduction in the number of relationship plots – focusing on most important endpoints.

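### SAP 9.10.1 uses the observed Week 12 trough as exposure for responses up to Week 48, with no rule for later dose changes, and conflicts with two other exposure definitions

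*SAP*

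**What the plan says.** SAP 9.10.1 opens with "The following Week 12, 24, 36 and 48 data will be plotted against SMT C1100 concentrations" and lists the responses: MRS fat fractions and T2, biopsy measures (Weeks 24 and 48 only) and functional scores. It then names the exposure: "For a visit, the above response will be plotted separately with relevant observed Week 12" C_trough, alongside simulated Cmax and Cav. The statistic is descriptive: "The Pearson correlation coefficients (for each week) will also be presented in the footnote of the plots". The section has no rule for boys whose dose changed after Week 12.

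Such boys can exist. Protocol 4.2.2 lets treatment be held after an intolerable event and then restarted at a lower twice-daily dose in Cohorts 1 and 3, "or reduce the frequency to once-daily dosing". Where a liver threshold is still met on repeat testing: "the study drug will be permanently stopped and may not be restarted although the patient will continue to be followed for functional and MRI assessments". SAP 5.1 keeps their data: "Data will be included in analyses regardless of the duration of time since their last dose of study treatment and the assessment". It adds that extra summaries leaving out assessments made several weeks after the last dose may be produced, case by case.

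Two other places define exposure differently. Protocol 12.1.4.2 says "Using a model exposure parameters will be predicted for each subject at the relevant visits", and that these values are to be used when exposure is related to other data. SAP 10.0, in its list of departures from the protocol, says "Instead the maximum concentration recorded at the relevant visit will be used in these analyses". SAP 5.5 has the population PK model predict Cmax, C_trough and Cav for each subject, and mentions no visit.

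**The concern.** Relating change in leg MRI to plasma concentration is a primary objective (Protocol 2.1, SAP 2.1). The protocol summary presents the concentration-response range as the way to identify plasma levels that may give benefit. The plots and correlations in SAP 9.10.1 are the only exposure-response outputs that this SAP specifies for that objective.

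The observed Week 12 trough is a single value, fixed before any later reduction, hold or stop. A boy stopped at Week 14 contributes his Week 48 MRI change at his on-drug trough, as if still treated. Whether the Cmax and Cav plots share the fault cannot be told, because the SAP does not say which visit or dose those values are simulated for. With three definitions in the current documents, two analysts could produce different answers to the same primary question and both claim to follow the plan.

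**Working it through.** The documents state no power, effect size or expected number of dose changes, so there is no planned figure to reproduce. The check has five steps.

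**1. The three rules side by side, for a boy stopped at Week 14 and assessed at Week 48**

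| Source | Exposure used | Reflects the stop? |
|---|---|---|
| Protocol 12.1.4.2 | Model-predicted at the relevant visit | Yes, if actual dosing is used |
| SAP 10.0 | Maximum concentration recorded at the relevant visit | Yes |
| SAP 9.10.1 | Observed Week 12 C_trough | No |
| SAP 9.10.1 | Simulated Cmax and Cav | Not stated |

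**2. One boy.** Stopped at Week 14, with exposure constant before and zero after: average over 48 weeks = 14/48 = 29% of his on-drug level. Halved at Week 12: (12 + 0.5 × 36)/48 = 30/48 = 62.5%. The second figure assumes dose-proportional exposure. Protocol 1.1.3 does not support that: the F2 study found no evidence that dose or regimen affected exposure, and F6 exposure rose more than proportionally between 0.5 g and 1 g bid. It is only an illustration.

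**3. Direction.** Let W be the Week 12 trough, E the actual exposure and Y the response. If Y = a + bE + error, with the error independent of W and E, then corr(W,Y) = corr(W,E) × corr(E,Y). Since |corr(W,E)| cannot exceed 1, |r| with W cannot exceed |r| with E. The sign reverses if corr(W,E) is negative. If b = 0 there is no bias. If dose changes follow the course of the disease, the independence fails and the direction is not fixed.

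**4. Size.** Simulation of 20,000 sets of 40 boys (about 30 + 10 in Cohorts 1 and 2). Exposure is lognormal with a CV of 78%, the lower end of the 78–248% in Protocol 1.1.3. Assumptions not in the documents: Cohort 2 exposure four-fold higher, true r = 0.40 with actual exposure, and the shares of boys changed. In the average-exposure column, the time of change is uniform between Weeks 12 and 48. Entries are the mean r at Week 48 using the Week 12 trough:

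| Boys changed after Week 12 | Current exposure drives response | Average exposure drives response |
|---|---|---|
| 10% at random, halved | 0.39 | 0.40 |
| 10% at random, stopped | 0.37 | 0.39 |
| 20% at random, stopped | 0.34 | 0.39 |
| Least exposed 10%, stopped | 0.40 | 0.40 |
| Most exposed 10%, halved | 0.37 | 0.39 |
| Most exposed 5%, stopped | 0.15 | 0.37 |
| Most exposed 10%, stopped | 0.04 | 0.36 |
| Most exposed 20%, stopped | -0.09 | 0.36 |

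The regression slope behaves differently. Relative to a true slope of 1, it was 0.80 to 0.97 for random changes under current exposure, up to 1.02 when the least exposed boys changed, and below zero when the most exposed 20% stopped.

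Timing matters too. A second simulation used 40 boys, CV 100%, a true r of -0.50 and average exposure driving response, with 2, 4 or 6 boys all stopped at Week 14:
- stopped at random: r = -0.49, -0.48, -0.46
- the most exposed boys stopped: r = -0.38, -0.33, -0.30

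With stop times spread evenly over Weeks 12 to 48 instead, the loss in r is about 1–3% for random stops, 7–11% for the most exposed boys, and nil for the least exposed.

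**5. Against sampling error.** The 95% interval for r = 0.40 with n = 40 is tanh(atanh 0.40 ± 1.96/√37) = 0.10 to 0.63. This is wider than the shift in most scenarios. The shift is systematic, however, and better data handling removes it.

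**The case against.** Five points can be made for the plan.

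- **C_trough is one of three metrics, and population PK has its own analysis plan** (SAP 9.9). This stands. A reader might infer that every exposure-response plot freezes exposure at Week 12. The documents do not show that: the basis of Cmax and Cav is unstated, not shown to be wrong. An unstated basis is still no safeguard.
- **SAP 10.0 already names a visit-specific metric.** True, and it would follow a dose cut. But it contradicts SAP 9.9 and 9.10.1. The same section records the Week 12 C_trough and simulated Cmax and Cav as an addition since SAP Version 2.0, so the maximum-concentration sentence may simply be left over.
- **SAP 5.1 allows summaries without late off-drug assessments, and SAP 9.4.1 lists dose regimens and tabulates reductions and stops.** These help. The summaries are optional, are decided case by case and do not cover dose reductions. The listings do not change the correlations.
- **High-exposure boys are not shown to stop more often.** This stands. The liver SAE in the F6 study arose at its lowest dose, 0.25 g bid (Protocol 1.1.3), and GLDH rises there were not dose dependent (Protocol 1.3.3). No boy in the F3 study SMT C11003 discontinued for an adverse event. The bilirubin/INR criterion does not apply to Cohort 1. One F6 boy did stop at 1 g bid for abdominal pain, so a link is possible but unproven.
- **The outputs are plots with footnoted correlations in an unpowered study.** True. This limits the consequence but does not justify a mismatched exposure.

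**Conclusion.** The point holds as a mismatch and a conflict. The observed Week 12 trough is paired with responses up to 36 weeks later (48 - 12), nothing adjusts it for dose changes, and three current passages define exposure differently.

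For boys with a dose change after Week 12, exposure is misstated, and the correlation for a primary objective can be weakened or distorted. The effect is small if changes are few, late or unrelated to exposure: in the first simulation, r goes from 0.40 to no lower than 0.34 with up to 20% of boys changed at random. It could be large if the most exposed boys stop early, particularly if current exposure drives the response. These sizes rest on assumed shares, timings and exposure distributions.

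A reader might infer that the plan is bound to push the result towards no relation, by a predictable amount. The documents do not support that. It requires response to depend on actual exposure alone, and a material loss further requires that the stopped boys are mainly the most exposed. Neither is established, and the sign and slope can also move in other ways. The change is worth making before the analysis because it is cheap and settles what exposure means.

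**What to change.** 1. Reconcile Protocol 12.1.4.2, SAP 9.10.1 and SAP 10.0 so that one exposure definition applies, and carry it into SAP 5.5 and 9.9.
2. For each response visit, use population-PK-predicted Cav and Cmax computed from the boy's actual dosing record: reductions, once-daily periods, holds, and no dosing after a stop. State in advance whether the main analysis uses exposure at the visit or averaged from Day 1 to it, and show the other as a sensitivity analysis. Both are needed because the protocol summary says it is unknown whether continuous or intermittent stimulation is required.
3. Keep the observed Week 12 C_trough as the matched metric for the Week 12 response only.
4. Mark on each plot the boys with a dose change or stop before that visit.

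Model-based exposure is preferable to substituting later observed troughs. In Cohorts 1 and 2, Weeks 24 and 48 are sampled around the PM dose and Weeks 12 and 36 around the AM dose (SAP 5.5), and Protocol 1.1.3 reports diurnal variation.

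The cost is SAP wording and further predictions from a model already planned, using dose regimens already recorded in the eCRF (SAP 9.4.1). The small downside is that exposure becomes model-based rather than observed.
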